Stroke/TIA	
 • Self-report • Coded on electronic medical records

	
• Brain imaging demonstrating previous ischaemic or haemorrhagic event
--	--

Withdrawal from Study

All participant derived data will be collected on the day of consent, bar the occasional case where a participant wishes to take the questionnaire home and post in back at a later date. Given the short period of time each participant will be actively enrolled in the study, it is highly unlikely a withdrawal of consent will occur. In the event of withdrawal of consent, a consent withdrawal form will be used to document this event. All data collected up to the date of consent withdrawal will be retained, but no further outstanding data collected. This will be made clear in the study information and consent form.

Statistical Analysis

Basic variables from CIED data

CIED data will be processed to create a new set of basic variables for analysis.

1. Mean daily physical activity (MDPA) – mean PA across dataset
2. PA intra-individual variability – as measured by:
 - Range
 - Interquartile range
 - Mean absolute deviation
3. PA surrounding NEHAs – multiple measures.

DOEDA = date of emergency department attendance; DOA = date of hospital admission; DOD = date of discharge; LOS = length of stay (DOD-DOA)

- Difference in PA from MDPA on DOEDA/DOA day -1, day -2, day-3, day-7, day -14
- Difference in PA from MDPA on DOEDA/DOD day +1, day +2, day+3, day+7, day +14
- ‘Time till PA recovery’ – time from DOEDA/DOD to day regained \geq MDPA

Descriptive analyses

All data will be stored and analysed using SPSS and ‘R’ statistical computing software. Basic descriptive statistics will be used to compare different sub-groups of participant (e.g. frail v non-frail). MDPA will be used to facilitate basic comparative analysis using a continuous variable. Determinants of MDPA will be calculated using univariate and multivariable analysis.

PA patterns

As demonstrated in *Figure 3* below, common activity patterns embedded within CIED PA data will be identified using clustering algorithms. Using these identified subtypes of PA as exposures in a longitudinal model with outcome NEHA, multilevel/hierarchical modelling methods (both classical and Bayesian approaches) will be utilised to investigate associations with outcome.

[figure not shown]

Figure 3

PA and major health events

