For this study, major health events are defined as NEHA episodes. Daily PA in the days leading up to NEHA episodes will be compared to a participant's MDPA, in order to define across the cohort when any observable change in PA is detected by this method. To explore trends in PA preceding NEHA episodes, a nested case control study will be constructed within the dataset, comparing trends in PA preceding NEHA episodes with general trends in PA before index times with no NEHA episodes. This will allow the creation of various 'PA markers' for diagnostic test evaluation methods (sensitivity/specificity, positive and negative predictive value). These PA markers will then be investigated to ascertain if they predict PA subtypes i.e. long-term behaviour patterns. We will also look at how these 'markers' superimposed on identified subtypes can be used to potentially personalise alert systems.

In a similar fashion, we will also explore PA trends following NEHA episodes. There is very little published data on 'recovery time' following hospitalisation episodes in an older population. This study is not powered to investigate this as a primary outcome, however we will measure 'time till PA recovery' following NEHA subtypes (A&E attendance and non-elective hospitalisation episodes), and examine determinants of this.

Risks to Study

Recruitment

A snapshot 'screening' audit using Cardex data in October 2016 found 341 potentially eligible patients on CIED annual follow-up at Manchester Royal Infirmary, an additional 150-250 patients at Wythenshawe are anticipated to be eligible. Recruitment will be undertaken by the PI. An 18-month period has been allocated for initial recruitment. Based on observational studies in similar population, we anticipate a take-up rate of from screening of between 60-80% (56).

Efforts made to maximise recruitment:

- Rigorous screening process
- Recruitment from existing clinical visits
- Low burden of assessment

In the event of lower than anticipated take-up, the recruitment window could be extended beyond 18 months to reach required sample size.

Missing data

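### 'Time till PA recovery' has no event-free benchmark, although a participant whose activity never changed would still 'recover' after about 2 to 3 days on average, and longer if daily activity is right-skewed

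*Combined protocol and SAP*

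**What the plan says.** Under Statistical Analysis, Basic variables from CIED data, MDPA is defined as "mean PA across dataset". Three sets of variables are built on it:

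- before the event: "Difference in PA from MDPA on DOEDA/DOA day -1, day -2, day-3, day-7, day -14";
- after the event: the corresponding differences on days +1 to +14;
- recovery: "time from DOEDA/DOD to day regained" to at least MDPA. No smoothing, tolerance band or run of days is required, so one day at or above the mean ends the wait.

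Under PA and major health events, the first use of these variables is direct: "Daily PA in the days leading up to NEHA episodes will be compared to a participant's MDPA". The stated purpose is to find, over all participants, the point at which a shift in activity first shows. No summary statistic or test is named. A nested case-control study follows, "comparing trends in PA preceding NEHA episodes with general trends in PA before index times with no NEHA episodes". For the period after the event the text says "In a similar fashion, we will also explore PA trends following NEHA episodes". It then adds that recovery time will be measured by NEHA subtype and its determinants examined, with the caveat "This study is not powered to investigate this as a primary outcome". No event-free index dates are stated for recovery time.

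**The concern.** A recovery time is naturally read as the time the event cost the participant. That reading needs an unaffected person to score at or near the minimum. Under this rule they do not. The clock stops on the first day at or above the participant's own mean, and such a day must be waited for even in an undisturbed series.

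Two things are at stake. Reported recovery times would include a component unrelated to the NEHA. The analysis of determinants is also exposed: anything that goes with day-to-day autocorrelation or with the shape of daily activity can appear as a determinant of recovery. More participants would not remove this, because it lies in the reference value and not in the precision.

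The pre-NEHA comparison with MDPA shares the weakness in a milder form. Whether zero is the no-change value there depends on a summary statistic that the plan does not name.

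**Working it through.** **Inputs.** From the documents: the definitions above; device storage of up to 14 months; about 51 expected NEHAs (Sample Size Calculations), which reproduces as 150 × 224/659 = 51.0. The documents give no distribution, variability or autocorrelation for daily activity. I therefore assume series of 365 days, lag-1 correlation 0 to 0.6 (on the underlying normal scale), and either a symmetric shape or a lognormal with log-SD s = 0.3 to 0.8. No event effect is present. The first day after the index date counts as day 1. If it were counted as 0, every mean below would fall by 1 and would still not be zero.

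**Recovery time, independent days.** Let p be the chance that a day is at or above the mean. The wait is geometric with mean 1/p, and the chance of more than 7 days is (1 − p)^7.

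- Symmetric: p = 0.5, so the mean is 1/0.5 = 2.0 days; more than 7 days, 0.5^7 = 0.8%.
- Lognormal: 1 − p = Φ(s/2).
  - s = 0.3: 0.560, mean 1/0.440 = 2.3 days; more than 7 days, 1.7%.
  - s = 0.5: 0.599, mean 1/0.401 = 2.5 days; 2.8%.
  - s = 0.8: 0.655, mean 1/0.345 = 2.9 days; 5.2%.

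**Recovery time with autocorrelation** (simulation of 20,000 participants per setting, MDPA taken from each participant's own series, placebo index date, lag-1 correlation 0.6):

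| Shape | Mean days | More than 7 days |
|---|---|---|
| Symmetric | 2.8 | about 8% |
| Lognormal, s = 0.3 | 3.3 | 10% |
| Lognormal, s = 0.5 | 3.7 | 13% |
| Lognormal, s = 0.8 | 4.4 to 4.5 | about 19% |

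So the delay exists without any skew. Autocorrelation alone adds 2.8 − 2.0 = 0.8 day. Skew alone adds 2.3 − 2.0 = 0.3 to 2.9 − 2.0 = 0.9 day when days are independent.

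**A different reference value.** If the median replaces the mean, p = 0.5 by construction. The null recovery time is then 2.0 days with independent days and 2.8 at lag-1 correlation 0.6. A log scale does no better: the log of a lognormal value is symmetric, so p is again 0.5.

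**Pre-NEHA difference from MDPA.** Under no effect the mean difference is about zero for any shape. Under the lognormal the median day differs from the mean by exp(−s²/2) − 1, which is −4% at s = 0.3, −12% at s = 0.5 and −27% at s = 0.8. With left skew the sign reverses. For 51 null dates and a within-person coefficient of variation of 0.3 to 0.7 (lognormal), a significant drop (nominal 2.5% in that direction) appears in 4% to 6% of t-tests, 9% to 23% of signed-rank tests and 14% to 42% of sign tests.

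**The case against.** The strongest reply has five parts.

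1. Right skew is not documented; the protocol itself says that little is known about normal day-to-day fluctuation. This stands. The upper figures for recovery time are conditional on it, but the 2.0 to 2.8 days are not.

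2. A reader might infer that Aim 4, the claim that activity drops before a NEHA, could be confirmed by skew alone. The documents do not support this. The plan names no median, rank or sign test, and a mean difference from MDPA has a null of about zero. The nested case-control study supplies NEHA-free index times for the pre-event trends, and the activity markers come from that comparison. Control times carry the same offset. Only the stand-alone comparison with MDPA lacks controls.

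3. A reader might also infer that skew would mimic moderation by frailty. Nothing in the documents allows this to be calculated. The variables are absolute differences, so less active participants could have a smaller offset in minutes even with stronger skew.

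4. Two features work the other way. MDPA has no stated exclusion of days around the event, which lowers the reference: by 7 × 0.8/365 = 1.5% for a week at 80% below usual, and by 35 × 0.5/365 = 4.8% for five weeks at half of usual. One isolated good day also counts as recovery. Both shorten recovery time, but neither makes its null value zero, and their sizes are unknown.

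5. Recovery is a secondary measure that the protocol says it is not powered for. That limits the consequence. It does not answer the point, since the problem is a reference value and not power. The wording that post-NEHA trends will be explored similarly might be meant to include controls, but it refers to trends, and nothing is stated for recovery time.

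**Conclusion.** The point holds for recovery time. Followed as written, the rule gives an unaffected participant a mean recovery time of about 2.0 to 2.8 days, assuming only a symmetric shape and lag-1 correlation between 0 and 0.6. If daily activity is right-skewed with log-SD 0.3 to 0.8, the range is about 2.3 to 4.5 days, with 2% to 19% taking more than 7 days. Without an event-free benchmark, the times and their determinants cannot be separated from ordinary variability and autocorrelation.

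For the pre-NEHA differences the point is narrower: the stand-alone comparison needs a named summary statistic and control dates, because under right skew a median, rank or proportion-below summary would show a spurious drop. It does not reach the case-control evaluation of predictive value. This should be corrected before analysis, but it does not threaten the study's main pre-event comparison.

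**What to change.** When the nested case-control index times are built, also draw NEHA-free index dates from the same participant, far enough from any NEHA that the day −14 to +14 window is clear. At those dates compute recovery time and all the MDPA differences by the same rules. Report each NEHA value against this within-participant benchmark, and examine determinants of the contrast and not of the raw time. State the summary statistic for the differences and which day counts as day 1 of recovery.

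Replacing MDPA by a median or a log scale would remove the skew offset in the differences but would leave the null recovery time at 2.0 to 2.8 days, so it is not enough alone.

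The cost is small: the index times have yet to be constructed, and the plan does not say that they come from the same participant, so that selection must be added along with some analysis code. No new data are needed.

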Data collection: daily PA measures, demographic details, co-morbidity status, physical frailty assessment, functional status, quality of life (QOL) and NEHA data

Consent: for participation in the study, physical frailty assessment, additional collection of retrospective CIED data, and access to electronic patient records

Data sources: CIED downloads, self-report questionnaire, physical measurements (height, weight, hand grip strength, gait speed), electronic hospital records, HES (hospital episode statistics) data

Results analysis: data will be analysed to investigate: daily PA variability; the association between PA and NEHAs, and the impact of frailty on PA patterns

Scientific and medical opportunities

This study will collect a unique set of new data for analysis. Combining expertise in Geriatric Medicine and Cardiology, this work will aim to provide a scientific basis for some of the fundamental assumptions made regarding health behaviours in later life. Little is known about normal day-to-day fluctuations in PA in an older population. This objective data will shed light on these patterns, and the temporal relationship between PA and NEHAs. Not only will this enhance our clinical knowledge, but it will provide the opportunity to develop proactive monitoring systems – potentially using PA as a proxy marker of health in certain older patient groups.

Expected outcomes

This study expects to find that NEHAs are commonly preceded by a demonstrable acute decline in PA. Various models will be tested to demonstrate predictive validity. This association is expected to vary by patient sub-groups defined by baseline health status (co-morbidity burden, degree of frailty), and demonstrated underlying activity pattern.

Further avenues for research

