By the nature of this study, participants are limited to those with a compatible CIED i.e. have some form of cardiac disease (the majority HF and/or conduction disorders). Cardiovascular disease is a fundamental pillar of ageing, lying on the spectrum of physiological frailty – inherent, and relevant to all older people (43). Therefore, on balance we do believe this population sample is generalisable to an older population with comparable functional status and degree of frailty. This study will be looking at temporal pattern analysis, using this population as a cohort of older people with a common age-associated long-term condition (heart disease). There is no reason to expect this group of patients would behave any differently with regard to PA and major health events compared with any other older patient group. Therefore we believe these results will be of interest out with the cardiac community.

Sample Size Calculations

Using data from previous analyses (21, 22) sample size calculations have been performed based on the Kesley and Fleiss formulas for 'cohort studies', using exposure = low/decline in PA and outcome = NEHA within 6 weeks. We considered a relative risk (RR) of 2.5-3 to be clinically significant in terms of a PA trigger signifying increased risk of NEHA. Sample size estimate thus = **150** participants (using inputs: 95% significance, 80% power, RR 2.5-3, output: 88 – 198, see *Table 1*).

Table 1: Sample size calculations

Variables	Option 1	Option 2	Option 3	Option 4
Two-sided significance level (1-alpha)	95	95	95	95
Power (1-beta, % chance of detecting):	80	80	90	90
Percent of Unexposed with Outcome:	17	17	17	17
Percent of Exposed with Outcome:	43	51	43	51
RR	2.5	3	2.5	3
Ratio of sample size, unexposed/exposed:	4.4	4.4	4.4	4.4
Sample size: Kesley	133	81	177	108
Sample size: Fleiss	145	88	198	121

The SENSE HF study (enrolling adult patients with chronic, stable HF, 6 months follow-up) captured 224 'unscheduled hospital visits' in 132 patients over 659 patient years, i.e. an annual rate of 34%. (44) Using this as a guide, with a sample size of 150 (150 patient years) we would expect to capture approximately 51 NEHA episodes from retrospective data collection.

Study Objectives

1. Describe the relationship between PA and NEHAs in an older CIED cohort
2. Describe daily variability of PA in an older CIED cohort
3. Describe the relationship between PA and NEHAs, and examining whether frailty moderates this relationship

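### Recovery time ends on a single day at or above a whole-record mean, so participants with a lasting loss of activity are often recorded as recovered

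*Combined protocol and SAP*

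**What the plan says.** Under Statistical Analysis, Basic variables from CIED data, time till PA recovery is the "time from DOEDA/DOD to day regained" at or above MDPA. The clock starts at the emergency department attendance or at discharge. MDPA is defined in the same list as "mean PA across dataset". The section PA and major health events speaks of a participant's MDPA, so the mean is each person's own, over all recorded days. PA is one value per day in the list of data to be collected.

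The word 'first' is not written, but a single day is named, and the natural coding is the first day that reaches MDPA. No section adds smoothing, a persistence requirement, a tolerance, or a rule for episodes that never reach MDPA.

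PA and major health events says the variable will be measured "following NEHA subtypes (A&E attendance and non-elective hospitalisation episodes), and examine determinants of this". It also says: "This study is not powered to investigate this as a primary outcome".

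**The concern.** A fluctuating daily series crosses a threshold by chance. If activity has settled at a lower level, an ordinary good day still ends the clock, and the recorded time then reflects day-to-day noise more than recovery. MDPA adds a second problem: post-event days are part of it, so a lasting drop pulls down the level that has to be regained.

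At stake are the recovery times themselves, which the protocol presents as a little-studied quantity, and the search for their determinants. Recorded times that are too short, and only weakly related to true recovery, would mislead on both.

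**Working it through.** The plan gives no figure for this variable, so there is nothing to reproduce. The documents also give no daily SD or autocorrelation. The Summary says: "Little is known about normal day-to-day fluctuations in PA in an older population". All SDs and lag-1 correlations (rho) below are therefore assumptions, shown as ranges.

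**1. Permanent deficit, no recovery.** Let activity settle d daily SDs below MDPA, with normal daily values. On independent days the daily chance of reaching MDPA is p = 1 − Φ(d), the chance of being 'recovered' by day k is 1 − (1 − p)^k, and the median day is ln 0.5 / ln(1 − p), rounded up.

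- d = 1: p = 0.159; median day 5; by day 7, 1 − 0.841^7 = 0.70; by day 14, 1 − 0.841^14 = 0.91.
- d = 2: p = 0.0228; median day 31; by day 14, 1 − 0.9772^14 = 0.275.

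With correlated days (20,000 simulated AR(1) series), the share 'recovered' by day 14 is:

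| Deficit | rho 0 | rho 0.4 | rho 0.7 | rho 0.9 |
|---|---|---|---|---|
| 1 SD | 91% | 84% | 69% | 47% |
| 2 SD | 28% | 25% | 19% | 11% |

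Right-skewed daily values (gamma, coefficient of variation 0.5) give 68% to 90% at 1 SD for rho 0 to 0.7. The problem is large for deficits up to about 1 SD and fades above that or at very high correlation.

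**2. Gradual true recovery.** Assumptions: 200 days before and 200 after the event; activity falls to 40–80% of baseline and climbs linearly; duration lognormal with median 30 days and log-SD 0.6; daily SD around 30% of baseline; rho 0 to 0.7; SD either constant or proportional to the current level. The current rule records a median of about 5 to 13 days. Its rank correlation with the true duration is 0.10 to 0.35.

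**3. Threshold.** A permanent 20% loss starting midway through the record gives MDPA = 1 − 0.2 × 0.5 = 0.90 of the pre-event mean. This comes on top of step 1, where the deficit was measured from MDPA itself.

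**4. Dependence on variability.** Take two groups of 26 and 25 episodes, since the Sample Size section says "we would expect to capture approximately 51 NEHA episodes from retrospective data collection". Give both the same distribution of true recovery time, rho 0 to 0.7, and compare recorded times by Mann-Whitney.

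- Drop unrelated to the person's SD: p<0.05 in 3–6% with equal SDs, 38–56% with SD 25% v 40%, and 88–98% with 20% v 50%. The more variable group 'recovers' sooner.
- Drop of 0.7 to 2 of the person's own SD, constant SD: 4–6%, so the effect vanishes.
- Same, with SD proportional to level: the direction reverses. At 20% v 50% and rho 0, medians are about 8 v 13 days, and between a third and a half of datasets reach p<0.05 across rho 0 to 0.7.

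**The case against.** The strongest reply is that the size rests on SDs and correlations the documents do not supply. That stands. The figures are conditional, and for deficits near 2 SD, or a 30% loss with SD 20% that scales with level (19–20% 'recovered' by day 14 at rho 0 to 0.4), there is little problem.

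A second reply is that the variable is one of several. Differences from MDPA at days +1 to +14 and the exploration of post-event trends would show a lasting deficit. They would, but they do not repair this variable, and the fixed-day differences use the same MDPA.

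A third is that recovery time is unpowered and belongs to none of the four objectives. That also stands and limits the weight of the point.

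Two stronger readings are tempting. One is that more variable participants always appear to recover sooner. Step 4 shows that this needs the size of the drop to be unrelated to the person's own SD; otherwise the effect can vanish or reverse, and the documents cannot settle which applies. The other is that a frail v non-frail comparison of recovery time will be spurious. Descriptive analyses gives that contrast only as a general example of sub-group description. The sub-division named for recovery time is by type of attendance, and the determinants are left open.

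**Conclusion.** The point holds in a limited form. As written, the rule lets one chance day end the clock and includes post-event days in its own threshold. If daily PA has low to moderate day-to-day correlation, most lasting deficits of up to about 1 daily SD would be recorded as recovered within two weeks, and a gradual recovery with a 30-day median would be recorded as about 5 to 13 days. These two results do not depend on how drop size relates to variability between participants. The direction of any bias linked to variability does, and is unknown.

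The effect is confined to the secondary recovery-time analysis and its determinants. The sample size and the planned analyses of PA before attendances are untouched. This is a cheap, optional improvement rather than a flaw that threatens the study.

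**What to change.** In Basic variables from CIED data, define recovery as a sustained return to the participant's pre-event mean. One example is the first 7-day mean at or above that mean, confirmed by the next non-overlapping 7-day mean. State which pre-event days form the baseline. Analyse as time-to-event, censored at device download, and say how a further attendance is handled. Report the single-day version as descriptive only, with 'first day' written in.

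Use a lower tolerance such as 90% only as a sensitivity analysis. In step 4 with drops that scale with own SD, the 90% rule gives p<0.05 in 11–60% without adjustment, partly because deeper drops truly reach 90% later, while the 100% rule stays at 4–7%.

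Include the participant's own variability in the determinants analysis. Mean absolute deviation is already planned under "PA intra-individual variability". Computing it on pre-event days keeps the post-event course out of the covariate.

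No new data are needed. The costs are:

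- timing resolved only to one or two weeks;
- 14 days needed to confirm recovery, and more censoring;
- a window length with no source in the documents;
- dependence on variability reduced, not removed: when drops are unrelated to SD, the unadjusted 100% rule still gives about 14–31% false differences at SD 20% v 50%, which is why the covariate is needed.

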Every day, a huge volume of physiological data, including daily PA, is routinely collected by most modern cardiac implantable electronic devices (CIEDs). These devices are fitted in patients with cardiac conduction disorders and/or heart failure (HF). The average age of a patient undergoing implantation of a CIED in the UK is approximately 70 year old (14, 15). Older people with CIEDs are a cohort of patients with a particularly high risk of clinical frailty, hospitalisation and mortality (16-19). This therefore makes an ideal population to study PA patterns and temporal relationships with major health events.

CIED remote monitoring

Modern CIEDs continuously collect data for a host of physiological parameters relevant to cardiac function, including; heart rate, rhythm and variability, thoracic impedance, pacing time and PA. This data is stored within the device until it is ‘downloaded’ for analysis (for up to 14 months). For example, the Medtronic CareLink® Network allows patients to manually download data via a home monitor system as well as automatic programmed downloads ordered by clinicians (usually every 3 months from home, and an annual hospital based CIED check). Reports are then forwarded on to care providers for action. PA is considered ‘low’ if patients are ‘active’ (defined as >70 steps/min) for less than 60 minutes over a 1-week period (non-overlapping).

Existing evidence

Algorithms using CIED data to predict impending healthcare utilisation (HCU) have been in existence for a number of years, but are not yet integrated into standard UK clinical practice. The PARTNERS-HF study (20) tested a prediction algorithm based on a combination of 8 parameters (AF duration, ventricular rate during AF, fluid index, patient activity, night heart rate, heart rate variability, % of pacing CRT and ICD shocks) in HF patients with CRT defibrillators. Patients with parameters outside the norm for 2 or more domains triggered an alert for clinical action. Cowie *et al.* 2013 expanded the PARTNERS-HF dataset, totalling 921 HF patients, mean age 67-68 years (21). 30-day HF hospitalisation rates in the high-risk group were 10 times higher than in the low risk groups, HR (hazard ratio): 10.0; 95% CI: 6.4–15.7, P, 0.001. ‘Low’ versus ‘high’ PA was the most common domain trigger, contributing to over 80% of high-risk alerts. Low PA as a single domain was associated with a 2-3 fold increased risk of HF hospitalisation (HR 2.5, P<0.001).

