A request will be made to DARS (data access request service, NHS Digital) for access to NHS Digital Hospital Episode Statistics (HES) data for each participant in the preceding 12 months. HES data will be requested twice during the study – at 6 months, and 18 months (a fee is associated with each request). HES data includes:

- Emergency department (ED) attendances
 - Date
 - Discharge destination
 - Main diagnostic codes from attendance
- Non-elective hospitalisation episodes
 - Date of admission
 - Date of discharge
 - Discharge destination
 - Main diagnostic codes from admission

- Discharge destination

Rationale for data collection process

Involvement of third party (Medtronic technical team)

Conversion of the CIED download file from .pdd to .xml format can only be done by Medtronic staff using internal software. Only pseudo-anonymised files will be shared with Medtronic. Please see data management plan (DMP) for further detail.

Use of USB stick

Transfer of data from the CIED processor to a computer can only be done using a portable USB stick.

Please see DMP for further clarification on data security.

Use of Southampton protocol for hand grip strength

The Southampton protocol for measuring handgrip strength is well established and has been used widely in large epidemiological studies involving older people. It is recommended by the European Working Party on Sarcopenia in Older People (49).

Use of HES data

MFT is a tertiary centre for Cardiology, therefore the local hospital for many device patients may be elsewhere within Greater Manchester. In order to ensure no NEHAs are missed, it is necessary to collect this data from NHS Digital, which monitors all hospital attendances on a national level.

Summary of data to be collected

Personal data (*hospital* records, self-report questionnaire)

1. Age (hospital records, verbally confirmed with patient)
2. Sex (self-report questionnaire)
3. Ethnicity (self-report questionnaire)
4. Postcode (hospital records)
 - 4.1. Index of deprivation measure
5. Type of accommodation (self-report questionnaire)
6. Living circumstances (self-report questionnaire)
7. Mobility aids (self-report questionnaire)
8. Care provision (self-report questionnaire)

Events/changes in care needs in preceding 12 months

9. Falls (self-report questionnaire)
10. Use of rehabilitation facilities in preceding 12 months (self-report questionnaire)
11. Frequency of use of primary care services (self-report questionnaire)

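### Time till PA recovery has no value when PA has not regained MDPA by the download, and no censoring rule is given, so completed-only results lean towards faster recovery (minor, secondary measure)

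*Combined protocol and SAP*

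**What the plan says.** Statistical Analysis, Basic variables from CIED data, lists time till PA recovery among the computed variables. It is the "time from DOEDA/DOD to day regained" MDPA or better, counted from emergency department attendance (DOEDA) or discharge (DOD). MDPA is defined in the same list as "mean PA across dataset".

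PA and major health events then states: "we will measure 'time till PA recovery' following NEHA subtypes (A&E attendance and non-elective hospitalisation episodes), and examine determinants of this". The same paragraph says the study is not powered for recovery as a primary outcome.

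Three other places fix the observation window:

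- Withdrawal from Study: "All participant derived data will be collected on the day of consent", apart from the occasional questionnaire posted back later.
- CIED remote monitoring: the device holds its data "for analysis (for up to 14 months").
- NEHA Episodes: DARS: hospital data are requested "for each participant in the preceding 12 months". No minimum gap between a NEHA and the visit is set.

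The analysis section names no time-to-event method, censoring date or value for an unrecovered episode. The Missing data section expects few gaps in device downloads. That is a different matter: the device series can be complete and the recovery day still lie beyond it.

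**The concern.** A duration that exists only once its end has been seen is right-censored. Here the end of observation is the clinic visit, and NEHAs can occur up to that day. Episodes without a value are those that happened late in the record, those that recover slowly, and those that never recover. Averaging the rest selects the quicker recoveries.

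The plan itself notes that little is published on recovery time after hospitalisation, so its estimate may be taken up by others. It also intends to compare NEHA subtypes and look for determinants. If one group truly recovers more slowly, it loses more episodes and the contrast between groups shrinks.

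**Working it through.** **The plan's own figure.** Sample Size Calculations takes 224 unscheduled visits from a cited heart-failure device study, "in 132 patients over 659 patient years, i.e. an annual rate of 34"%, and applies the rate "with a sample size of 150 (150 patient years"). 224/659 = 0.340 per patient-year, and 150 × 224/659 = 50.99, so the stated figure of about 51 NEHAs reproduces.

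**Assumptions.** The documents give neither recovery times nor a never-recover share. I assume that NEHA dates are uniform over L = 365 days before download and that recovery is exponential with median m, so λ = ln 2 / m.

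**Share with no value, if everyone eventually recovers:** (1 − e^(−λL)) / (λL).

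- m = 30: λL = 8.433, share = 0.9998/8.433 = 0.119.
- m = 60: λL = 4.217, share = 0.9853/4.217 = 0.234.

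**Completed-only median:** the t that solves (1 − e^(−λt)) − [(1 − e^(−λt))/λ − t·e^(−λt)]/L = half the share observed. For m = 30 and t = 26.3 the left side is 0.4554 − 5.39/365 = 0.441, and the right side is (1 − 0.119)/2 = 0.441.

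| True median (days) | Share lost | Of 51 NEHAs | Completed-only median (days) | Shortfall |
|---|---|---|---|---|
| 7 | 3% | 1.4 | 6.8 | 3% |
| 14 | 6% | 2.8 | 13.2 | 6% |
| 30 | 12% | 6.1 | 26.3 | 12% |
| 60 | 23% | 11.9 | 45.1 | 25% |
| 90 | 33% | 17.0 | 57.8 | 36% |

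Simulation gives the same values, and log-normal recovery (sigma 1) gives similar ones: 26.6 days at a true median of 30, and 47.0 at 60.

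**If a share p never recovers,** the true median over all episodes is −ln(1 − 0.5/(1 − p))/λ, and the loss is p + (1 − p) × share above. The completed-only median does not move.

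- p = 10%, m = 30 in the rest: true 35 days, completed-only 26; 21% lost (10.5 of 51).
- p = 20%, m = 30: true 42 days, completed-only 26; about 30% lost (15.0 of 51).
- p = 20%, m = 60: true 85 days, completed-only 45; 39% lost (19.7 of 51).

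**Contrast between groups.** True medians of 60 and 30 days (ratio 2.0) become 45.1 and 26.3 (ratio 1.7).

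**How often would the plan's own threshold go unmet?** As written, one day at or above MDPA is enough, and MDPA includes the days after the NEHA. Suppose activity falls permanently by a fraction d, with D days left in the record, pre-event mean 1 and normal daily values with a constant coefficient of variation (CV). Then MDPA = 1 − dD/365. The daily chance of reaching it is P = 1 − Φ((MDPA − (1 − d))/(CV(1 − d))), and the chance of no value is (1 − P)^D. With d = 0.4, D = 90 and CV = 0.5: MDPA = 0.90, P = 0.158, median day ln 0.5/ln 0.842 = 4, and no value is almost impossible. Averaged over D = 1 to 365, with CV 0.5 and 0.3, the loss is:

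- 20% drop: about 1%;
- 40% drop: 2% and 9%;
- 60% drop: 21% and 46%.

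With log-normal daily activity the corresponding losses were about 1%, 3-6% and 11-31%.

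**The case against.** The best reply is that the plan nowhere says unrecovered episodes will be excluded. It gives an origin and an event, and an unnamed analysis of determinants could be a survival analysis. That is true, so this is an omission with a predictable consequence, not a stated decision to discard data. The consequence still follows if the variable is computed as listed.

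Second, the bias may be negligible. With medians of 7-14 days and full recovery, 1 to 3 of 51 episodes are lost, and the lenient threshold makes long or absent recoveries less common than clinical experience would suggest. This stands for small and moderate drops, but not for large ones that last.

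Third, non-recovery is not invisible: differences from MDPA at days +1 to +14 are also recorded, and only about 51 × 14/365 = 2 NEHAs would fall within 14 days of download. This too stands, although those measures do not give a recovery time.

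Some stronger readings are tempting but unsupported:

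- A reader might infer that someone readmitted before recovering has no value. They do have one if MDPA is regained before download; what is missing is a rule for attributing it.
- A reader might take the shortest usable record, 98 days (six months in situ, about 182 days, less the 84 excluded after implantation), as typical. It is an eligibility edge: recruitment is from annual follow-up and planning assumes one patient-year each.
- A reader might conclude that recovery will be most overstated in the frail or after admission. That requires slower recovery in those groups, on which the documents give no figures.

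**Conclusion.** The point holds as a minor correction. Time till PA recovery is right-censored at the download, the plan provides no way of handling that, and a completed-only summary errs towards faster recovery. Under uniform NEHA dates over 365 days and exponential recovery, the median is 3-6% too short when the true median is 7-14 days and all recover, 12% at 30 days and 25% at 60 days, and worse if some never recover. The one-day, whole-record threshold will usually keep the loss near the low end, except after large drops that are slow to recover or permanent.

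Recovery time is not among the four study objectives and is acknowledged as unpowered, so the main PA-NEHA analyses are untouched. Lack of power excuses imprecision but not a systematic lean in one direction.

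**What to change.** In Basic variables from CIED data and in PA and major health events:

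- Define recovery as a time-to-event outcome for every NEHA, from DOEDA or DOD, censored at the download date.
- Report the number not recovered, with Kaplan-Meier or cumulative incidence curves by NEHA subtype.
- Examine determinants with a model that allows censoring, such as Cox regression with standard errors clustered by participant, kept to few terms given about 51 events.
- State how a further NEHA before recovery is handled. A competing-event analysis is one option and not a requirement.

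The cost is wording only, since download and NEHA dates are already collected. Intervals will be slightly wider than for a completed-only summary, and a median may not be reached in some subgroups.
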